### **3.3.2 Follow-up for withdrawn subjects**

If subjects need to be withdrawn from the study based on the above reasons, they will transition to following the clinical standard of care that is medically required for their particular situation. The block that is in place will be unblinded to the physician and patient. Unblinding will help the physician and patient understand if it may be worth trying to continue with the block in such circumstances as a means of pain control. Continuation with the blinding procedures could only delay achievement of adequate pain control and removal of unnecessary hardware, if the block ends up containing the control—normal saline. The remainder of the hospital course for these withdrawn subjects will continue according to standard medical practice. Their course will continue to be tracked for research purposes and they will be included and reported in the study results.

## **4.0 Recruitment Methods**

### **4.1 Identification of subjects**

The urology surgeons and members of the research team will identify potential study candidates as they present to the urology clinic to discuss their upcoming surgery. Identification of potential subjects can occur both prior to clinic by using the patient medical record, as well as at the patient clinical encounter.

### **4.2 Recruitment process**

After identification of potential subjects, at their clinic visit, the urology surgeons will confirm their eligibility and interest in participating. Study information and a copy of the consent form will be provided to the patient to review. Official enrollment of eligible and interested patients will occur in the urology clinic by the end of their preop visit. Consent to participate in the study will formally be obtained during this visit by a member of the research team. Attestation of the subject enrollment/consent will be signed by the principal investigator.

### **4.3 Recruitment materials**

Patient consent form

### **4.4 Eligibility/screening of subjects**

All potential subjects will be screened for initial study eligibility according to the inclusion and exclusion criteria, listed above—3.1,.3.2, during their urology clinic visit prior to their scheduled surgery.

## **5.0 Consent Process and Documentation**

### **5.1 Consent Process**

#### **5.1.1 Obtaining Informed Consent**

##### **5.1.1.1 Timing and Location of Consent**

Written consent will take place in the urology clinic following confirmation of patient eligibility and agreement to participate in the research study.

##### **5.1.1.2 Coercion or Undue Influence during Consent**

It will be explained to the patient that research is voluntary. The patient will be encouraged to ask questions and it will be explained to the patient that their decision to participate or not participate will have no effect on their level of care.

#### **5.1.2 Waiver or alteration of the informed consent requirement**

Not applicable

### **5.2 Consent Documentation**

#### **5.2.1 Written Documentation of Consent**

Written consent will be obtained. The patient will retain a signed and dated copy. A signed and dated copy will also be stored in the locked office of the research team and stored in the patient's medical record.

#### **5.2.2 Waiver of Documentation of Consent (Implied consent, Verbal consent, etc.)**

Partial waiver requested for review of schedules/charts for recruitment purposes.

### **5.3 Consent – Other Considerations**

#### **5.3.1 Non-English Speaking Subjects**

Not applicable

#### **5.3.2 Cognitively Impaired Adults**

##### **5.3.2.1 Capability of Providing Consent**

Not applicable

##### **5.3.2.2 Adults Unable To Consent**

Not applicable

##### **5.3.2.3 Assent of Adults Unable to Consent**

Not applicable

#### **5.3.3 Subjects who are not yet adults (infants, children, teenagers)**

##### **5.3.3.1 Parental Permission**

Not applicable

##### **5.3.3.2 Assent of subjects who are not yet adults**

Not applicable

## **6.0 HIPAA Research Authorization and/or Waiver or Alteration of Authorization**

### **6.1 Authorization and/or Waiver or Alteration of Authorization for the Uses and Disclosures of PHI**

**Check all that apply:**

Not applicable, no identifiable protected health information (PHI) is accessed, used or disclosed in this study. [Mark all parts of sections 6.2 and 6.3 as not applicable]

- Authorization will be obtained and documented as part of the consent process. [If this is the only box checked, mark sections 6.2 and 6.3 as not applicable]**
- Partial waiver is requested for recruitment purposes only (Check this box if patients' medical records will be accessed to determine eligibility before consent/authorization has been obtained). [Complete all parts of sections 6.2 and 6.3]**
- Full waiver is requested for entire research study (e.g., medical record review studies). [Complete all parts of sections 6.2 and 6.3]**
- Alteration is requested to waive requirement for written documentation of authorization (verbal authorization will be obtained). [Complete all parts of sections 6.2 and 6.3]**

## **6.2 Waiver or Alteration of Authorization for the Uses and Disclosures of PHI**

### **6.2.1 Access, use or disclosure of PHI representing no more than a minimal risk to the privacy of the individual**

#### **6.2.1.1 Plan to protect PHI from improper use or disclosure**

Information is included in the "Confidentiality, Privacy and Data Management" section of this protocol.

#### **6.2.1.2 Plan to destroy identifiers or a justification for retaining identifiers**

Identifiers will be destroyed by unlinking the subject ID code numbers from their MRNs and deleting this information from the database. This will occur following full analysis and publication.

### **6.2.2 Explanation for why the research could not practicably be conducted without access to and use of PHI**

Use of PHI is necessary to identify eligible patients and link them to their clinical data.

### **6.2.3 Explanation for why the research could not practicably be conducted without the waiver or alteration of authorization**

Waiver of Authorization is requested for assessing patient eligibility prior to review of the consent document and enrollment in the research study.

## **6.3 Waiver or alteration of authorization statements of agreement**

Protected health information obtained as part of this research will not be reused or disclosed to any other person or entity, except as required by law, for authorized oversight of the research study, or for other permitted uses and disclosures according to federal regulations.

The research team will collect only information essential to the study and in accord with the 'Minimum Necessary' standard (information reasonably necessary to accomplish the objectives of the research) per federal regulations.

Access to the information will be limited, to the greatest extent possible, within the research team. All disclosures or releases of identifiable information granted under this waiver will be accounted for and documented.

## 7.0 Study Design and Procedures

### 7.1 Study Design

The study will be prospective, randomized, controlled, and double blinded.

### 7.2 Study Procedures

After study approval and prior to study start, [name] will be responsible for educating the clinical head nursing staff of the inpatient wards, Same Day Unit (SDU) and Post Anesthesia Care Unit (PACU) of this study and its protocol requirements. She will also provide an educational session to both the division of Urology as well as to the department of Anesthesiology on the study and protocol requirements.

#### 7.2.1 Day 1 –Screening and Consent

The urology surgeon and/or study coordinator will identify potential patients according to the inclusion/exclusion criteria (3.1-3.2) prior to or on the day of clinic. These will be patients scheduled for surgery using a flank or anterior subcostal incision. A copy of the consent form will be provided to the subject at the time of their clinic visit. Patient eligibility and interest in participation will be confirmed by the urology surgeon at the clinic visit prior to surgery. If they meet the criteria to be included into the study, a member of the research team will obtain written consent from the patient during this preop clinic visit.

#### 7.2.2 Working Day prior to surgery

A member of the research team will call the patient to ensure that they are planning on coming in for their scheduled surgery (i.e.: not sick, running a fever, has transportation). Members of the research team who will perform the block will be notified to confirm coordination of this procedure in the Same Day Unit (SDU).

The subject will then be randomized by the study statistician using a computer-generated randomization list using SAS software (SAS Institute, Cary, NC) into two groups:

- Group 1. Erector spinae plane block (ESPB)
- Group 2. Sham Erector spinae plane block. (SESPB)

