## 3.3 Early Withdrawal of Subjects

### 3.3.1 Criteria for removal from study

1. If the block cannot be placed/technically performed in the patient
2. If the subject does not follow protocol
3. If they are unable to participate cognitively after the surgery.
4. Any inpatient Clavian III or greater surgical complication
5. If surgery needs to be carried out via an incision other than flank or anterior subcostal
6. If the subject has an adverse event, such an allergic reaction attributed to the study drug, causing the patient to become unblinded
7. If the patient has pain requirements which exceed all options available in this protocol.

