#### 7.2.3 Day of Surgery - Pre-op

**In the SDU**, [name] will be present to ensure the current surgery and anesthesia team for the study patient are sufficiently educated on the protocol requirements and to ensure safety and protocol adherence. The patient will receive a study bracelet with the study ID and patient's specific randomization ID. The block procedure will be performed in the SDU by a member of the anesthesia block team, who is also part of the research team. The placement of the erector spinae catheter will occur according to standard practice guidelines using strict sterile conditions and is similar regardless of type of study medication that the patient will be randomly receiving. After the block catheter is placed, a member of the research team will pick up the study drug from the pharmacy, deliver it to the SDU and ensure the correct coordination of study drug to the patient using the patient's study ID bracelet. The ESP catheters will be bolused with 20 ml of Ropivacaine 0.5% vs 20ml of normal saline (placebo). Following this initial bolus, the ESP catheter will be connected to a pump containing Ropivacaine 0.2% or normal saline which will

deliver automatic boluses of 15ml of either study medication or normal saline every 3 hours. The automatic bolus dosing of 0.2% Ropivacaine is based on the standard dosing for all adults weighing between 50-120kg.

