#### **7.4.3 Method for Assigning Subject to Treatment Groups**

On the working day prior to surgery, subjects consented for the study will be randomized from a computer-generated randomization list using SAS software (SAS Institute, Cary, NC) and using block stratification with block sizes of two and four to allow an equal number of participants in each of the study groups.

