**19.6 Unblinding Procedures**

Unblinding of the study drug would occur if a patient developed an adverse reaction, such as an allergic reaction, attributed to the study drug. Documentation of the adverse reaction would ensue and the patient would be unblinded and then withdrawn from the study. Such a patient would then be cared for in context of standard medical practice and their remainder of their medical course would continue to be tracked for research purposes and reported in final study results. Additionally, in any instance that the subject is being withdrawn from the study, as listed in section 3.3.1, the subject will also be unblinded. Unblinding will help the physician and patient engage in a more meaningful and effective clinical interaction for pain control. There will be no confusion as to if the block may or may not contain active medication, Ropivacaine, and thus could be effective for the clinical scenario.

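### Randomising the working day before surgery means patients whose catheter cannot be placed are randomised, unblinded and reported without receiving either study treatment; assigning the number after placement avoids this

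*Combined protocol and SAP*

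**What the plan says.** Timing of randomisation is stated twice and consistently. Section 7.2.2, after the telephone call to the patient: "The subject will then be randomized by the study statistician using a computer-generated randomization list using SAS software". Section 7.4.3: "On the working day prior to surgery, subjects consented for the study will be randomized from a computer-generated randomization list using SAS software". The list uses blocks of two and four. Sections 7.4.5 and 7.4.6.3 then have the unblinded investigational pharmacy package and label the drug with the patient's randomisation number.

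The catheter comes later, in the Same Day Unit on the day of surgery (7.2.3): "The block procedure will be performed in the SDU by a member of the anesthesia block team, who is also part of the research team". Placement "is similar regardless of type of study medication that the patient will be randomly receiving". Only then is drug collected: "After the block catheter is placed, a member of the research team will pick up the study drug from the pharmacy".

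The first criterion for removal in 3.3.1 is: "If the block cannot be placed/technically performed in the patient". Section 19.6 adds that "in any instance that the subject is being withdrawn from the study, as listed in section 3.3.1, the subject will also be unblinded". Section 3.3.2 says withdrawn patients go on being tracked and appear in the study results. Section 8.2 raises 17 per group to 20 to cover withdrawals. Section 8.3 specifies a two-sided t-test for the primary endpoint and names no analysis set.

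**The concern.** Successful catheter placement is in effect an eligibility condition, but it is applied after randomisation. Nothing done to the patient before the catheter is in depends on the allocation, so the order is not forced by the treatment itself.

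Two things are at stake. The first is efficiency. A patient with no catheter carries no information on ropivacaine against saline. Kept in the comparison, such patients pull the arms together; left out, they use up an allowance of three per group that also has to cover the six other removal criteria in 3.3.1.

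The second is blinding. The patient is told the allocation before a self-reported pain score on postoperative day 1, although no study drug was given. The reasons the plan gives for unblinding do not fit: 3.3.2 speaks of a block that exists ("The block that is in place will be unblinded to the physician and patient"), and 19.6 of whether that block might contain active drug. With blocks of two and four at a single centre, each needless disclosure also gives away something about neighbouring allocations; in a block of two it fixes the other one.

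**Working it through.** **Inputs.** From 8.1 and 8.2: 20 randomised per group, 17 per group required, difference 2 points, SD 2 in each group, two-sided alpha 0.05, power 80%. The rate p of failed placement is not in the documents. I assume 5%, 10% and 15%, equal in both arms; 15% equals the plan's whole allowance (3/20).

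**The plan's own figure.** Power comes from the noncentral t distribution with 2n − 2 degrees of freedom and noncentrality δ/(σ√(2/n)).
- n = 16: 2/(2√(2/16)) = 2.828, power 78.1%.
- n = 17: 2/(2√(2/17)) = 2.915, power 80.7%. So 17 is the smallest n that reaches 80%, and the stated figure is reproduced.
- 17/0.85 = 20 per group, also reproduced.
- n = 20 with no losses: 2/(2√(2/20)) = 3.162, power 86.9%.

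**Failures kept in as randomised, with no drug effect.** The expected difference becomes 2(1 − p). The active arm is now a mixture with variance 4 + 4p(1 − p), the control arm keeps variance 4, and the working SD is √((8 + 4p(1 − p))/2).
- p = 5%: difference 1.9, SD 2.024, noncentrality 2.969, power 82.5%.
- p = 10%: difference 1.8, SD 2.045, noncentrality 2.784, power 77.4%.
- p = 15%: difference 1.7, SD 2.063, noncentrality 2.606, power 71.9%.

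Holding the SD at 2 gives 83.3%, 79.2% and 74.5%.

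**Failures excluded.** The number left in each arm is binomial (20, 1 − p), and power is averaged over it.

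| Assumed failure rate | Expected failures of 40 | Power, kept in | Power, excluded | Chance both arms keep at least 17 |
|---|---|---|---|---|
| 0% | 0 | 86.9% | 86.9% | 100% |
| 5% | 2 | 82.5% | 85.0% | 96.8% |
| 10% | 4 | 77.4% | 82.8% | 75.2% |
| 15% | 6 | 71.9% | 80.3% | 42.0% |

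Every row counts placement failure alone. With the number assigned after placement, this cause takes no randomised patients: power starts at 86.9% whatever p is, and the full three per group remain for other withdrawals.

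**The case against.** The strongest reply is that this concerns efficiency, rests on an assumed rate, and is already budgeted for. Much of that stands. Scoliosis is an exclusion and the operator belongs to the anesthesia block team, so failures may be rare. If failures are excluded, power stays at or above 80% across the assumed range. At about 5% it stays above 80% even with failures kept in.

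Several stronger readings are tempting but not supported:
- **That early randomisation biases who fails placement.** Technique does not depend on the drug and the drug arrives afterwards, so with a blinded operator failure should be unrelated to arm.
- **That the trial is underpowered.** That would need a failure rate the documents do not give.
- **That failures will certainly dilute the primary test.** Section 3.3.2 includes withdrawn patients in the results, but 8.3 does not say whether they enter the t-test.
- **That patients found unfit on the morning of surgery meet the same fate.** Section 3.3.1 has no such criterion, and the unblinding rule in 19.6 is tied to that list.

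There is also a practical reason for the present order: the pharmacy prepares numbered syringes and cartridges in advance, and its preparation time is not stated. The study statistician does the randomising, and the bracelet carrying the randomisation ID is described before the block. These points shape the fix but do not remove the case for it, because drug is already collected after placement. It is also true that the missing analysis set is a wider gap covering all seven removal criteria. Filling it, however, would only choose between dilution and lost numbers for these patients, whereas later assignment avoids both.

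**Conclusion.** The point holds as an avoidable inefficiency and a needless unblinding, worth correcting because correction is cheap. For assumed failure rates of 5% to 15%, power at 20 per group drops from 86.9% to 82.5%–71.9% with failures kept in, or to 85.0%–80.3% with failures excluded. These figures rest on the plan's difference of 2 and SD of 2, on equal failure in both arms, on no drug effect in patients without a catheter, and on no other withdrawals. The true rate could be lower and the loss then small. The sequence from randomisation to unblinding does not depend on that rate: it follows from the text for any patient whose catheter cannot be placed.

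**What to change.** 1. In 7.2.2, 7.4.3, 7.4.5 and 7.4.6.3, state that the next number on the concealed, pre-generated list is assigned only once the catheter is in place. The statistician supplies the list and the pharmacy assigns from it on the morning of surgery.
2. In 7.4.5 and 7.4.6.3, allow the pharmacy to prepare the next numbered blinded kit the day before. If placement fails, the kit is held for the next patient or discarded, and the number stays unassigned.
3. In 7.2.3 and 7.4.4, have the randomisation ID added to the bracelet after placement and then checked against the kit label.
4. In 3.3.1, make failure to place the catheter a pre-randomisation screen failure, counted and reported as such. A technical failure after assignment stays under 3.3.1 and is analysed as randomised; say so in 8.3.
5. In 19.6, state that patients who received no study drug are not unblinded.

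The cost is wording in these sections, pharmacy cover for number assignment on the morning of surgery, and an occasional unused kit. No additional randomised patients are needed, and the order of placement and drug collection does not change. The sponsor should confirm with the pharmacy that its preparation time fits. The change does not deal with the other removal criteria, which still need a stated analysis set.

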#### 7.2.3 Day of Surgery - Pre-op

**In the SDU**, [name] will be present to ensure the current surgery and anesthesia team for the study patient are sufficiently educated on the protocol requirements and to ensure safety and protocol adherence. The patient will receive a study bracelet with the study ID and patient's specific randomization ID. The block procedure will be performed in the SDU by a member of the anesthesia block team, who is also part of the research team. The placement of the erector spinae catheter will occur according to standard practice guidelines using strict sterile conditions and is similar regardless of type of study medication that the patient will be randomly receiving. After the block catheter is placed, a member of the research team will pick up the study drug from the pharmacy, deliver it to the SDU and ensure the correct coordination of study drug to the patient using the patient's study ID bracelet. The ESP catheters will be bolused with 20 ml of Ropivacaine 0.5% vs 20ml of normal saline (placebo). Following this initial bolus, the ESP catheter will be connected to a pump containing Ropivacaine 0.2% or normal saline which will

deliver automatic boluses of 15ml of either study medication or normal saline every 3 hours. The automatic bolus dosing of 0.2% Ropivacaine is based on the standard dosing for all adults weighing between 50-120kg.

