### **7.4 Test Article(s) (Study Drug(s) and/or Study Device(s))**

#### **7.4.1 Description**

Ropivacaine Hydrochloride injection 0.2% is FDA approved for use in surgery as a field block (infiltration) regional anesthesia. We will use the Penn State Health standard of care ambulatory pump to provide the automatic and demand boluses of the study drug through the ESP catheters.

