#### **7.4.2 Treatment Regimen**

Group	Drug mixture
ESPB	Ropivacaine 0.2%
SESPB	Normal saline

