### **7.4.6.3 Preparation and Dispensing**

Following randomization of study patients (randomization will occur the working day prior to scheduled operative date), the study drug will be packaged both in a syringe which will contain the initial bolus dose and also in a cartridge which will contain the automatic pump boluses. Both the syringe and cartridge which will be nonspecific to the medication type (Ropivacaine or Normal saline). The syringe and cartridge will be labeled both with the study ID and the patient's specific randomization number. The ESPB syringe and cartridge will contain Ropivacaine 0.2% and the SESPB syringe and cartridge will contain normal saline. All preparation, dispensing of drug into cartridges and cartridge labeling will occur by the investigational pharmacy, who will remain unblinded. The day of surgery, a member of the research team will pick up both the syringe and cartridge and deliver it to the SDU. Here, the syringe followed by the cartridge will be connected to the block catheters allowing administration to begin in the SDU.

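### The loading bolus is ropivacaine 0.5% in section 7.2.3 but 0.2% in section 7.4.6.3, a 2.5-fold difference in dose

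*Combined protocol and SAP*

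**What the plan says.** - **Section 7.2.3** sets the load: "The ESP catheters will be bolused with 20 ml of Ropivacaine 0.5% vs 20ml of normal saline (placebo". It then moves to the pump: "Following this initial bolus, the ESP catheter will be connected to a pump containing Ropivacaine 0.2% or normal saline". The pump is to "deliver automatic boluses of 15ml of either study medication or normal saline every 3 hours". Read alone, 7.2.3 describes a stronger load followed by a weaker maintenance solution.
- **Section 7.4.6.3** describes the preparation. First, "the study drug will be packaged both in a syringe which will contain the initial bolus dose"; the pump solution goes in a separate cartridge. Then the contents: "The ESPB syringe and cartridge will contain Ropivacaine 0.2% and the SESPB syringe and cartridge will contain normal saline". It gives no syringe volume.
- **Section 7.4.1** describes the product: "Ropivacaine Hydrochloride injection 0.2% is FDA approved for use in surgery". The table in **7.4.2** gives 0.2% for the active group. Neither mentions 0.5%.
- **Section 7.2.5** has the pump stop for good once the study-drug total reaches 770 mg. It does not say whether the syringe load is part of that total. It also says that the principal investigator will write order sets specific to the study.

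**The concern.** The load is part of the treatment under test, and its dose is stated twice with different values. The clinical procedure and the pharmacy instruction concern the same syringe, so a pharmacy that follows one departs from the other. Nothing elsewhere in the protocol says which governs.

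A mismatch would not show at the bedside. On identification the protocol says "The syringe and cartridge will be labeled both with the study ID" (and the randomization number), and the check in 7.4.4 matches identifiers, not strength.

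What is at stake is the definition of the active regimen. A report that takes its dose from 7.2.3 when the pharmacy worked from 7.4.6.3 would state 100 mg when 40 mg was given, and the reverse error is equally possible. Anyone repeating the regimen would not know which load was tested.

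**Working it through.** The plan gives no mg figure for the load, so there is none to reproduce. The inputs are the volume and strength in 7.2.3, the strength in 7.4.6.3, the pump settings in 7.2.3 and the 770 mg limit in 7.2.5. A 1% solution holds 10 mg per ml, so 0.5% is 5 mg/ml and 0.2% is 2 mg/ml.

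**Load**
1. Under 7.2.3: 20 ml × 5 mg/ml = 100 mg.
2. Under 7.4.6.3, with the 20 ml of 7.2.3: 20 ml × 2 mg/ml = 40 mg.
3. Ratio: 100 / 40 = 2.5. Difference: 100 − 40 = 60 mg.
4. For scale, one automatic bolus is 15 ml × 2 mg/ml = 30 mg every 3 hours, so the gap equals 60 / 30 = 2 scheduled boluses.

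**Can the sections be reconciled?**
1. By volume: 100 mg at 0.2% needs 100 / 2 = 50 ml, which is not the 20 ml of 7.2.3.
2. By taking 0.2% to mean the cartridge alone: 7.4.6.3 names syringe and cartridge as separate items and gives 0.2% for both.
3. By majority: 7.4.1 and 7.4.2 give 0.2% only, which favours 7.4.6.3. But 7.2.3 states two strengths in consecutive sentences, 0.5% for the load and 0.2% for the pump, so its 0.5% looks deliberate. Either section could be the slip.

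**Lock-out**

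The limit is in mg, so for saline it can operate only as a volume of pump solution. At 2 mg/ml the options are:

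| Load counts toward 770 mg? | Left for the pump | Pump volume |
|---|---|---|
| No | 770 mg | 770 / 2 = 385 ml |
| Yes, 40 mg load | 770 − 40 = 730 mg | 730 / 2 = 365 ml |
| Yes, 100 mg load | 770 − 100 = 670 mg | 670 / 2 = 335 ml |

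If the load does not count, the permitted total including the load is 770 + 40 = 810 mg or 770 + 100 = 870 mg.

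**The case against.** The best defence is that practice will settle the matter. The trial has one site, one investigational pharmacy does all preparation and labeling, and 7.2.5 provides for study-specific order sets. One strength is therefore likely to be fixed for all 20 patients in the active group. That stands, and it limits the consequence. It does not remove the conflict, because the protocol does not show what the order set says, and whichever strength it uses will contradict 7.2.3 or 7.4.6.3.

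On the lock-out, the defence is that the natural reading is already clear: 7.2.5 describes a pump limit, and the load comes from a separate syringe before the pump is connected. That also largely stands. A clarifying sentence is worth adding because the wording refers to total study drug, but this is not a second contradiction.

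A reader might infer more than the documents support:
- **That the active arm will mix two doses.** Nothing in the protocol suggests that practice would vary between patients, and the safeguards above point the other way.
- **That the primary endpoint is affected by a known amount.** If the load is given by noon (an assumption; no start time is stated), it precedes the 9AM opening of the pain-score window on postoperative day 1 by at least 21 hours. The documents give no duration of action, so the gap in mg cannot be turned into a gap in pain score.
- **That packaging without a visible drug identity is a fault.** It is the intended blinding, and the unblinded pharmacy knows the contents.
- **That the cap spoils the study-drug total on postoperative day 3.** Any dose cap bounds a cumulative dose. How often it would bind depends on start time, demand use and whether the first automatic bolus comes at connection or 3 hours later, none of which the protocol gives. Reporting how many patients reached the cap is a preference, not the correction of an error.

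**Conclusion.** The contradiction is real and rests on the text alone: 7.2.3 and 7.4.6.3 give different strengths for the same loading syringe. The 2.5-fold ratio in mg assumes only that the 20 ml of 7.2.3 applies to the syringe in 7.4.6.3, which states no volume. The documents do not show which strength was intended.

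The expected harm is modest: a protocol that contradicts itself on an operative dose, and a report that may state the wrong one. The documents do not support a claim of a mixed arm or of a biased primary comparison, and neither the sample size nor the primary test depends on this point. It should be corrected because the dose of the test treatment has to be unambiguous. Whether the load counts toward 770 mg is a minor clarification to make at the same time.

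**What to change.** 1. State one loading-bolus volume, strength and mg dose, in the same words, in 7.2.3, 7.4.6.3 and the 7.4.2 table. The choice of strength is the investigator's. If 0.5% is intended, 7.4.6.3 should give 0.5% for the active syringe and 0.2% for the active cartridge, and 7.4.2 should list both. If 0.2% is intended, 7.2.3 should say so and give the load as 40 mg (at 20 ml).
2. Make the study order set match.
3. Add one sentence to 7.2.5 saying whether the syringe load counts toward 770 mg, and give the resulting pump volume, identical in both arms: 385 ml if it does not count.

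The cost is wording in four sections and a check of the order set. It needs no new data collection and no change to the cap, the sample size or the analysis.
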